## **8. RESEARCH INFORMATION IN MEDICAL RECORDS**

No research data will be included in the subject's medical record for this study.

#### **Frequency of Data and Safety Monitoring**

The PI will be informed of serious adverse events as soon as they occur by the study coordinator and will notify the RSRB, NIH Program Officer, and the Data Safety Monitoring Board (DSMB) within 48 hours of becoming aware of the event. The PI will report the Serious Adverse Events and Unanticipated Problems to the RSRB within 5 business days of becoming aware of the event, according to local RSRB requirement. Specific triggers for an ad hoc review or initiation of the process of an ad hoc review will occur if there are unforeseen deaths or the threshold for SAE has been met.

Safety reports are sent to the Data Safety Monitoring Board twice a year and will include a detailed analysis of study progress, data and safety issues.

#### **Content of Data and Safety Monitoring Report**

The study report will contain the following documents and tables:

- Actual versus expected enrollment table, including a CONSORT diagram.
- Table of testing results, including number of tests per student or staff member, testing outcome (positive, negative) for both Serology and RT-PCR
- Table of aggregate adverse events, deaths, and unanticipated problems
- Demographic data will include sex, ethnicity, race, education and age and will be stratified by site.
- Table of expected and missing visits, time points, and tests
- Table of protocol deviations

#### **Monitoring Body Membership and Affiliation**

The following individual(s) has/have accepted position(s) as part of the Data Safety Monitoring Body (DSMB). DSMB membership will be reviewed and approved by the University of Rochester Research Subjects Review Board (RSRB). Should there be any questions regarding the independence of the DSMB it will be addressed and corrected if necessary.

### **Conflict of Interest for the DSMB Members**

Monitoring body members should have no direct involvement with the study investigators or intervention. Each member will sign a University of Rochester Conflict of Interest Statement which includes current affiliations, if any, with any steering committees or advisory councils associated with the study, pharmaceutical and biotechnology companies (e.g., stockholder, consultant), and any other relationship that could be perceived as a conflict of interest related to the study and/or associated with commercial or non-commercial interests pertinent to study objectives.

### **Protection of Confidentiality**

Only deidentified and/or masked data will be presented during the open sessions of the DSMB. All data, whether in a report or discussed during a DSMB meeting are confidential. Participant identities will be kept confidential unless safety concerns necessitate unmasking some or all data.

### **Monitoring Entity Responsibilities**

The responsibility of the Monitoring Board will include:

- Reviewing the research protocol, Data and Safety Monitoring Plan (DSMP), and informed consent documents, proposed revisions.
- Evaluating the progress of the study on an ongoing basis including periodic assessments of data quality, participant recruitment, accrual and retention, participant risk versus benefit, and other factors that can affect the outcome.
- Considering the impact of factors external to the study when new information, such as scientific or diagnostic developments becomes available that may affect safety of participants, their willingness to participate in the study or the ethics and conduct of the study.
- Reviewing Unanticipated Problems, Serious Adverse Event.
- Reporting any problems with study conduct or performance to the UR Research Study Review Board.
- Ensuring the measures to ensure the confidentiality of study data and results are appropriate.
- Reviewing and evaluating requests for protocol modifications/amendments.
- Reviewing before study initiation the stopping rules and plans for interim analyses presented in the protocol. These plans outline the conditions under which a study may be stopped (e.g., difficulties in recruitment, retention, obtaining outcome measures or other issues).
- Reviewing the interim analyses and/or accumulating data at the specified interval(s), and as appropriate and make a recommendation to continue, terminate or modify the study based on observed benefit or harm in accordance with the planned stopping rules.

**Principal Investigator:**

**[name]**

**Department of Neuroscience**

## **DATA and STATISTICAL ANALYSIS**

Primary data analysis will focus on understanding the spread of COVID-19 in a school for children with Intellectual and developmental Disabilities. By testing both students and staff in the school, and understanding interactions of staff and students throughout the day we aim to understand risk and develop risk mitigation techniques to help the school better reduce outbreaks and risk of infection. Based on blood samples we will also study the immune response of students and staff both to vaccination and also to infection. The time course of the immune response will be evaluated. Information about immune responses and infection will be conveyed to families and staff in order to encourage vaccination and also to help them understand how they may be putting their students and families at risk. Longitudinal and regular virological testing will track infection rates, and serological testing will quantify the durability of protective immunologic responses, which may be shorter-lived in IDD populations.

Statistical analyses will be performed using SPSS, or other similar software. Descriptive statistics will describe the incidence rates of COVID infection in participants, and the immunity levels of the students and staff (based on serological testing). Network modelling and agent-based simulations will be used to interactively test mitigation strategies. Qualitative surveys of participants will facilitate understanding of key community concerns, myths, and misconceptions about vaccination, with a goal of developing a multimodal educational campaign that addresses these concerns.

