#### **1.4 CENTRAL AIMS**

**Scientific Goal 1: Establish a molecular testing program to monitor and identify COVID-19 infections within a school community of individuals with IDD**

**Overview and rationale:** This program will focus on the students (n=450) and staff (n=500) of the MCC, who collectively form a community that is highly representative of other IDD school communities across the nation. We will establish testing across this difficult-to-test population, using a tailored and flexible approach to foster test uptake and to prevent and/or mitigate COVID-19 outbreaks.

**Establish a clinical molecular and serological COVID-19 testing program for the Mary Cariola Center:** The dynamics of viral spread are unknown in a school serving individuals with IDD such as the MCC. Questions to be answered with *molecular* testing include: What is the incidence of asymptomatic COVID-19 infection, and how is this affected by rising vaccination rates? How do activities within the school alter risk? *Serological* testing will assess baseline prevalence of prior infection (anti-NP IgG), and changes over time, in response to infection (anti-NP IgG+) and vaccination (anti-S IgG+, anti-NP IgG-).

**Molecular Testing:** RT-PCR tests for SARS-CoV-2 with FDA EUA will deliver highly sensitive and specific clinical-grade results. Respiratory samples will be obtained by mid-turbinate or nasal swabs, collected in a dedicated area with proper ventilation and PPE (see Mobile Unit testing plan below), and delivered to the URMC Central Laboratory for testing in a CLIA environment with 24-72h turnaround times. The testing plan includes two groups: those tested as part of scheduled surveillance and those tested for symptoms or exposure.

**Surveillance Screening and Exposure/Symptomatic Testing:** Participants will be tested every 5-14 days to increase likelihood of detecting infected but asymptomatic individuals. Enrolled students and staff who report symptoms in the on-site screening will be tested on-site. Symptomatic individuals will be tested separately from asymptomatic participants every 3 days for up to 10 days. *Reported* test results will be qualitative, although Ct (cycle threshold) values will also be captured for modeling purposes.

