*Network modeling* – We will contrast both a **contact network** and a **mobility network model (Fig 2)**. Data used for modeling will include the instruction schedules of IDD-students, staff and class locations. Each data record will contain the subject ID, activity, location, time, and duration. Student and staff attributes will be stored in the secure BLIS informatics database system (see Facilities and Resources), which will also hold the COVID-19 PCR and serology testing results. We will also incorporate anxiety data from the PROMIS survey (Goal 5 below), and rates of prior infection/vaccination (derived from serology data). We will use the schedule database to construct directed, bipartite graphs where the nodes represent two categories of individuals (students, staff), and the edges are weighted by the duration of contact (4, 6). A **mobility network model** (1, 2) (**Fig. 2B**) will capture the movement of students and staff between physical locations within the building. For both network models, we will characterize measures of network structure (density, diameter) (1, 4, 6), and identify individuals with high contagion centrality. We will simulate various testing frequencies of asymptomatic individuals (1). For example, we will model outcomes for increasing testing for: (1) staff who contact many students to decrease transmission risk, (2) staff who connect groups of students to decrease between-group spread. Sensitivity analysis will assess how modification of parameters (e.g. vaccination proportion, asymptomatic viral load) affects the ability to detect infection.

[figure not shown]

Figure 2

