**Contingency Plans:** During COVID, MCC has had to respond to immediate changes in requirements from DOH and the NYS Governor. The process to "pivot" will be replicated, as it has worked well within the organization structure. Upon notification of a change, this will be broadly communicated to the project team, with same day conference established to evaluate and implement required changes. We anticipate during the course of this study that vaccinations will be approved for children under 16. This opportunity will be incorporated into educational initiatives, and will be recorded for study participants. Our scientific goals as outlined herein have built in contingencies around the expected introduction of vaccines in this population. We will also work with NIH program to revise the research and testing program in response to major changes in policy. The modeling goal described above is specifically designed to react to changing infection/vaccination landscapes.

**Community Partnerships and Engagement:** Our goal is to enroll 70% of eligible students and staff at MCC. This enrollment projection is based on past local experience of [name] and the MCC leadership, and the high motivation level of MCC parents/guardians and staff. To increase participant engagement and interest in the project we will modify our proposed student recruitment and retention approaches based on key input and feedback from MCC leaders and a convenience sample of parents/guardians (9, 10). Our approach will start with an Introduction Phase followed by an Engagement phase, concluding with a Consent phase that includes baseline (and follow-up) surveys to characterize the participants, their households and community of residence. The UR Clinical and Translational Science Institute (directed by MPI [name]) will assist, and has extensive experience in community engagement, recruitment and retention of special populations. The IDDRC Human Phenotyping and Recruitment (HPR) Core will also be leveraged for their expertise including recruiter training and retention strategies.

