## 2. CHARACTERISTICS OF THE RESEARCH POPULATION

### 2.1 Subject Characteristics

All staff and students at Mary Cariola Center (MCC) are eligible for this study

**a) Number of Subjects** – There are 500 on-site staff and 450 students. Up to 950 people may enroll, although we expect around 70% enrollment

**b) Gender and age of subjects** – Among MCC **employees**, approximately 75% are female. We expect at least 50% to consent to testing and another 30% to complete the baseline survey.

**Among students under age 18**, approximately 30% are female, consistent with the national IDD population. We expect 70% to enroll. Unless our enrollment trends show otherwise we do not anticipate any unique messaging or additional outreach to achieve our enrollment target. There are also Mary Cariola students age 18-21 approximately 30% female.

**There are no exclusions by age** however we are limited by the ages of those attending or residing in MCC and the age range of employees.

**MCC students** are included in this study as the main participants as the study seeks to understand testing and transmission patterns among individuals with IDD in school and residential settings including modeling. Most of the students in the school setting are under age 18; The youngest student is age 3. There are also about 60 students at the school between the ages of 18-21. Approximately one third of these students have legally authorized representatives (guardians).

Age distribution of students is:

3-5	20%
6-10	28%
11-14	25%
15-17	19%
18-21	8%

We will track early enrollment to determine if rates are lower than expected or if there are under-represented age groups (based on the age distribution of MCC students). This will warrant revising of recruitment strategies and tactics within the research team and the CAB.

**MCC Staff** range in age from 18 to 75.

STUDY #: 5294

Version Date: 04/17/2023

Page 9 of 27

Efforts to enroll employees will be informed by the CAB. We will track early enrollment to determine if rates are lower than expected or if there are under-represented age groups. Lower than anticipated enrollment will warrant revising of recruitment strategies and tactics within the research team and informed by the CAB.

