## **Genetic Research Procedures**

*Banking of DNA samples for mRNA vaccine response and IgG level decay targeted genotyping:*

**Blood Sample** - One tube (one tube – 6-10ml) of blood will be collected from up to 200 neurotypical staff and 50 IDD students and stored for later DNA isolation and targeted genomic analysis. This is genomic research and NOT genetic testing. It will be carried out for research purposes only and no information about genetics will be disseminated to participants. After all testing is completed samples will be destroyed.

Population (Minor vs. Adults)	Blood Draw Procedure (COVID antibodies, MBC, or DNA)	Amount of Blood	Frequency of Blood Draw	Fingerstick or Venipuncture
Adults	COVID anti	1-2 drops	monthly	fingerstick
Minors	COVID anti	1-2 drops	monthly	fingerstick
Adults	COVID	6-10 cc	Every 6 months (completed)	Veni.
Minors	COVID	6-10cc (unless under age 5 (then 3- 5cc)	Every 6 months (completed)	Veni.
Adults	MBC	6-10 cc	Once only	Veni.
Minors	MBC	6-10cc (unless under age 5 (then 3- 5cc)	Once only	Veni.
Adults	DNA	6-10cc	Once only	Veni.
Minors	DNA	6-10cc (unless under age 5 (then 3- 5cc)	Once only	Veni.

**Mandated COVID-19 testing for Mary Cariola Staff:** In response to the New York State vaccine mandate Mary Cariola Center policy requires **staff who are not vaccinated** to be tested weekly for COVID-19. One method for meeting this policy requirement is enrollment in this study. Staff who are enrolled will be tested weekly and results reported to Mary Cariola personnel. **For all unvaccinated staff enrolled in the study** missing the scheduled weekly COVID test will be reported to Mary Cariola administrative personnel in accordance with Mary Cariola Center policy.

**Other data.** MCC will also provide student and staff schedules (i.e. what room they are in) for use in the modeling

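### Enrollment can satisfy a work rule that applies only to unvaccinated staff, so unweighted staff immunity and the model inputs drawn from it may not reflect the staff as a whole

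*SAP*

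**What the plan says.** The SAP (Data and Statistical Analysis) states the estimator in one sentence: "Descriptive statistics will describe the incidence rates of COVID infection in participants, and the immunity levels of the students and staff". Incidence is confined to participants. Immunity is worded for the students and staff, and the protocol's second goal (section 1.3) likewise aims at background immunity in both groups rather than in enrollees.

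Protocol section 4.1, in the paragraph on mandated staff testing, reports a school policy that requires unvaccinated staff "to be tested weekly for COVID-19". It adds: "One method for meeting this policy requirement is enrollment in this study". For unvaccinated staff who enroll, "missing the scheduled weekly COVID test will be reported to Mary Cariola administrative personnel". No comparable requirement is stated for vaccinated staff. The general schedule in section 1.4 reads: "Participants will be tested every 5-14 days to increase likelihood of detecting infected but asymptomatic individuals".

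On numbers, section 2.1 says "There are 500 on-site staff and 450 students" and expects half or more of the employees to agree to testing. The community engagement paragraph of section 1.4 gives a higher figure: "Our goal is to enroll 70% of eligible students and staff at MCC".

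Scientific Goal 3 lists among the inputs to the network models "rates of prior infection/vaccination (derived from serology data", and names the vaccination proportion as a parameter to vary in sensitivity analysis.

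Neither document mentions weighting, standardisation, reporting these estimates by vaccination status, or comparing enrolled with non-enrolled staff on vaccination. Section 2.1 watches enrollment only for low rates and under-represented age groups.

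**The concern.** Vaccination status is a main determinant of measured immunity, and it may also affect the risk of infection. If it also affects who joins, an unweighted staff summary mixes two things: how immune the staff are, and who had a reason to enroll. The policy gives unvaccinated staff a reason both to join and to keep their test appointments.

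Two outputs are exposed. The first is the description of staff immunity, which is worded for the staff and not only for those enrolled. The second is the set of infection and vaccination rates that the school models take from serology. Those models represent student and staff contact and movement across the school, while 30% to 50% of staff would be outside the sample at the enrollment levels the protocol gives. A skewed vaccination mix would carry through to the simulated testing and mitigation strategies.

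**Working it through.** The documents give no vaccination split for the school's staff and no bias figure, so there is nothing to reproduce. The check is selection arithmetic.

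**Inputs from the documents**
- Staff: 500 (section 2.1).
- Overall staff enrollment, E: 50% (section 2.1, stated as a minimum for testing) or 70% (sections 1.4 and 2.1).

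**Assumptions**
- Unvaccinated share of staff, U: 15%. This borrows the 85% vaccine uptake quoted under Scientific Goal 5 for the university medical center, a different workforce. The 40% hesitancy quoted there before outreach serves as an upper case.
- Share of unvaccinated staff who enroll, e: 70% or 90%.
- Infection rate ratio, unvaccinated to vaccinated, RR: 2 or 3.

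**Formulas**
- Unvaccinated share of the sample: s = U × e / E.
- Implied enrollment of vaccinated staff: v = (E − U × e) / (1 − U), and relative enrollment r = e / v.
- Ratio of sample incidence to all-staff incidence: (1 + (RR − 1)s) / (1 + (RR − 1)U).

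**Results at U = 15%**

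| E | e | r | s | Shift (points) | Incidence overstated, RR = 2 | RR = 3 |
|---|---|---|---|---|---|---|
| 50% | 70% | 1.51 | 21.0% | +6.0 | 5.2% | 9.2% |
| 50% | 90% | 2.10 | 27.0% | +12.0 | 10.4% | 18.5% |
| 70% | 70% | 1.00 | 15.0% | 0 | 0% | 0% |
| 70% | 90% | 1.35 | 19.3% | +4.3 | 3.7% | 6.6% |

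Example, second row: s = 0.15 × 0.90 / 0.50 = 0.27; v = (0.50 − 0.135) / 0.85 = 0.429; r = 0.90 / 0.429 = 2.10; for RR = 2, 1.27 / 1.15 = 1.104; for RR = 3, 1.54 / 1.30 = 1.185. At RR = 1 the incidence bias is zero in every row.

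**Upper case, U = 40%, using s = Ur / (Ur + 1 − U).** At r = 1.5, s = 0.60 / 1.20 = 50.0% (+10.0 points). Incidence is overstated by 1.5 / 1.4 − 1 = 7.1% at RR = 2 and by 2.0 / 1.8 − 1 = 11.1% at RR = 3.

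**Reversed case, r = 0.8.** At U = 15%, s = 0.12 / 0.97 = 12.4% (−2.6 points). At U = 40%, s = 0.32 / 0.92 = 34.8% (−5.2 points). The sample then holds too few unvaccinated people, and at U = 15% with RR = 2 incidence is understated by 2.3% (1.1237 / 1.15 = 0.977).

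**Immunity.** If a fraction a of vaccinated and b of unvaccinated staff are seropositive, the bias in seroprevalence is −(s − U)(a − b). The shift in vaccination share is therefore its upper limit in size, reached only if a = 1 and b = 0. Prior infection raises b and shrinks the bias. Vaccine-derived immunity alone would read 73% to 79% against 85% at E = 50%, and 80.7% to 85% at E = 70%.

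**Effect of standardising.** Weights U/s for unvaccinated and (1 − U)/(1 − s) for vaccinated participants return the unvaccinated share to U. The usual approximate variance inflation is U²/s + (1 − U)²/(1 − s). At s = 21% it is 0.107 + 0.915 = 1.02, and at s = 27% it is 0.083 + 0.990 = 1.07.

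**The case against.** The strongest reply is that the direction is not shown. Enrolling is only one way to comply. It asks more than a weekly swab, because staff must accept antibody testing (section 2.2), with monthly fingersticks and six-monthly venipuncture (section 4.1). Scientific Goal 5 ties mistrust to hesitancy about both testing and vaccines. All staff are paid (section 4.4) and monitored free of charge (section 6.2), so vaccinated staff also have reasons to join. This stands: a reader might infer that the sample will hold too many unvaccinated people and that immunity is biased down, but the documents support only that this may happen. Testing hesitancy is a weaker counterweight than it looks, since unvaccinated staff must be tested somewhere.

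The size is also open. The 50% figure is a minimum; at 70% enrollment the shift is between 0 and 4.3 points in the cases above. The 50% rows need unvaccinated staff to enroll at 1.5 to 2.1 times the vaccinated rate, which no section supports.

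The SAP limits incidence to participants, and a crude rate describes participants correctly. Its use as a model parameter is implied at most. Students, 450 of the 950 people, are outside the staff policy, so no school-wide immunity bias of the size shown for staff follows.

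Finally, Scientific Goal 3 already plans to vary the vaccination proportion, and its agents carry individual vaccine status. That softens the modeling point, but it neither corrects the central value nor gives a source for the status of staff who do not enroll.

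**Conclusion.** The concern holds as a possible, unaddressed selection bias linked to vaccination status. It bears on the staff immunity description and on the serology-derived rates used in the models. It bears on incidence only when the participant rate is taken as the rate for all staff.

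Size and sign are unknown. With 15% of staff unvaccinated and 70% to 90% of them enrolled, the unvaccinated share of the sample is 21% to 27% at 50% staff enrollment and 15% to 19% at 70%. Incidence is then overstated by 5.2% to 10.4% or by 0% to 3.7% at a rate ratio of 2, and by 9.2% to 18.5% or by 0% to 6.6% at a ratio of 3. Lower enrollment among unvaccinated staff reverses the sign. The bias in seroprevalence is smaller than the shift in vaccination share, to the extent that unvaccinated staff have infection-derived antibodies.

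A reader might also infer that time trends are distorted from the start of the mandate. The documents date neither the mandate nor the enrollments, so this cannot be established. The point is a worthwhile, inexpensive improvement and does not invalidate the study.

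**What to change.** In the SAP:

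- Report staff immunity and incidence separately by vaccination status.
- Obtain aggregate staff-wide vaccination counts from the school, by calendar period if available, and standardise the staff estimates to them. Show the unweighted figures alongside.
- Use the staff-wide vaccination proportion as the staff input to the models, in place of the proportion seen in participants.
- If the counts cannot be had, report by vaccination status and give a sensitivity range over plausible staff vaccination shares.

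The same standardisation corrects the mix whichever way it is skewed. The cost is a data request and a modest loss of precision (about 2% to 7% in variance at 50% enrollment in the cases shown). The school's policy implies that it knows who is unvaccinated, but the documents do not say that it will supply counts, hence the fallback.

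Standardising assumes that, within each vaccination group, enrollment is unrelated to infection or immunity. It does not correct differences in test frequency: unvaccinated staff are tested weekly, about 52 times a year, while the general interval of 5 to 14 days gives 26 to 73. Detection may therefore still differ between the groups, and the report should say so.
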